2.1. Ethical Approval

The study protocol was reviewed and approved by the Research Ethics Committee of the Faculty of Dentistry, King Abdulaziz University, Jeddah, Saudi Arabia (Approval No. 169-11-24). Written informed consent was obtained from all parents or legal guardians prior to participation, in accordance with the Declaration of Helsinki.

2.2. Study Design

This study was designed as a randomized, controlled crossover clinical trial. Each participant used both interdental cleaning methods, water flossing and regular flossing, in two separate visits with a 14-day washout period between interventions to minimize carryover effects.

2.3. Study Setting

The study was conducted at the College of Dentistry and the University Dental Hospital, King Abdulaziz University, Jeddah, Saudi Arabia. Participant recruitment and data collection took place between November 2024 and April 2025.

2.4. Sample Selection

Participants were recruited using a convenience sampling approach from patients attending the College of Dentistry and the University Dental Hospital at King Abdulaziz University. Eligible participants who met the inclusion criteria were enrolled after obtaining informed parental consent.

2.5. Randomization

2.5.1. Sequence Generation

Random allocation sequences were generated using an online randomization tool (<https://www.randomizer.org>). Two sets of random numbers were created, corresponding to the two intervention orders.

2.5.2. Allocation Concealment

Each allocation code was printed, cut into identical slips, and sealed in opaque envelopes. The envelopes were placed in a single container. Upon recruitment, each participant selected one envelope to determine their assigned intervention sequence.

2.6. Blinding

Due to the nature of the interventions, blinding of the participants and operators was not feasible. However, the statistician responsible for data analysis was blinded to the group assignments to minimize analytical bias.

2.7. Inclusion and Exclusion Criteria

The inclusion criteria included children aged 10-15 years, medically fit and systemically healthy, with no active orthodontic treatment or space maintainer with no use of any type of dental floss within the previous 24 hours. Children with fewer than four posterior proximal contacts were excluded from the study.

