2.9. Study Procedures

Participants were screened according to the inclusion and exclusion criteria. Parents were informed that participation was voluntary and that all collected data would remain confidential and accessible only to the research team.

Each participant was randomly assigned to start with one of the following:

- Group A: Unflavored, unwaxed regular dental floss (Oral-B, USA)(Figure 1a), or
- Group B: Water flosser (Waterpik Cordless Plus Water Flosser, USA)(Figure 1b).

After the first visit, a 14-day washout period was observed before the crossover intervention was applied.

At the first visit, demographic data (participant initials, age, and sex) and group allocation were recorded. A clinical examination was performed to assess the Plaque Index (PI) using the criteria of Silness and Le (1964). All participants received standardized oral hygiene instructions, including brushing twice daily with the Modified Bass Technique using a soft-bristled toothbrush and fluoridated toothpaste. Participants received instructions on the proper use of the assigned interdental cleaning method and performed the procedure independently.

The Plaque Index (PI) was recorded for all teeth according to the following criteria:

- 0: No plaque in the gingival area.
- 1: A film of plaque adhering to the free gingival margin and adjacent tooth area, detectable only by a probe.
- 2: Moderate accumulation of soft deposits visible to the naked eye within the gingival margin.
- 3: Abundant soft matter within the gingival pocket and/or along the gingival margin.

At the second visit, participants switched to the opposite cleaning method (water flosser or regular floss), and plaque scores were reassessed using the same PI criteria.

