2.10. Statistical Analysis

Descriptive statistics, including means, medians, standard deviations, interquartile ranges (IQRs), minima, and maxima, were calculated to summarize the data. Normality was assessed using the Kolmogorov-Smirnov test, and Levene's test was conducted to evaluate the assumption of equal variances. Due to the violation of the normality assumption, the Wilcoxon signed-rank test was used for the comparison of plaque scores between water floss and regular floss. This test was also used for additional paired comparisons, including before and after flossing, anterior versus posterior teeth, maxillary versus mandibular arches, and right versus left sides.

Linear regression analysis was used to assess the association between gender and plaque scores after flossing for each flossing method, with adjusted

models controlling for age and number of surfaces flossed. The significance level was set at $p\text{-value} = 0.05$. All analyses were performed using Stata version 16.1 (StataCorp, College Station, TX). (a)

(a)

(b)

Figure 1. Oral hygiene aids used in the study: (a) Regular dental floss (Oral-B, USA); (b) Water flosser (Waterpik Cordless Plus Water Flosser, USA).

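### Time since last toothbrushing is neither fixed nor recorded before the scored visits, which may cost the paired water-versus-string comparison some precision and headroom, of unknown size and without systematic bias

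*Combined protocol and SAP*

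**What the plan says.** Section 2.7 admits children "with no use of any type of dental floss within the previous 24 hours". It is an eligibility criterion, it concerns floss only, and Section 2.9 does not repeat it for the second visit.

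On brushing, Section 2.9 says: "All participants received standardized oral hygiene instructions, including brushing twice daily with the Modified Bass Technique using a soft-bristled toothbrush and fluoridated toothpaste". This is given at the first visit. It covers frequency and technique, not when the last brushing should fall relative to an examination. The visit-1 items listed are demographics, allocation and the Plaque Index; time of last brushing is not among them. The second visit is described in one sentence: "At the second visit, participants switched to the opposite cleaning method (water flosser or regular floss), and plaque scores were reassessed using the same PI".

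The outcome is scored 0 to 3 on all teeth at the gingival margin. Score 1, for example, is "A film of plaque adhering to the free gingival margin and adjacent tooth area, detectable only by a probe".

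The design is a crossover "in two separate visits with a 14-day washout period between interventions to minimize carryover effects" (Section 2.2). In Section 2.10, "the Wilcoxon signed-rank test was used for the comparison of plaque scores between water floss and regular floss". No adjustment for pre-floss score, period or time since brushing is stated. The before-and-after comparison is a separate test: "This test was also used for additional paired comparisons, including before and after flossing". The regressions concern gender and adjust for age and number of surfaces flossed.

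**The concern.** The 24-hour floss rule shows that the plan wants recent interdental cleaning kept out of the score. Children are also told to brush twice a day, and nothing controls how recently they did so when plaque is scored.

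A crossover gains precision by cancelling what is stable within a child. Time since brushing is a property of the visit. If a child comes soon after brushing on one occasion and many hours after on the other, that difference goes straight into the paired difference. The 14-day gap is aimed at carryover from the first method and does nothing about this.

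Two losses are possible: a wider spread of paired differences, and, where starting plaque is low, less for either method to remove. That plaque varies with time since brushing is inferred from what the index measures. The documents give no figure for it.

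**Working it through.** **Inputs from the plan (Section 2.8).** 44 participants, 22 per group, 80% power, two-sided 0.05. The effect size comes from a cited study and is not stated; no SD or within-child correlation is given.

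**Assumed inputs.** The paired-difference SD apart from brushing is 0.25 index points. Starting plaque varies uniformly with time since brushing over a range R of 0.3, 0.6 or 0.9. A fraction k = 0.5 of that variation remains after flossing. The brushing-related components at a child's two visits have correlation ρ of 0, 0.5 or 0.8.

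**Step 1: the plan's own figure.** Without an effect size, 44 cannot be reproduced forwards. Solving backwards with the noncentral t distribution:
- 44 pairs: standardised paired difference dz = 0.432
- two independent groups of 22: d = 0.865

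The plan does not say which calculation was run. For the signed-rank test at 0.955 efficiency the paired value is 0.443, so the t-based figures are close enough here.

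**Step 2: added noise.** The per-visit SD of a uniform range is R/√12, so

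added SD = k × √(2(1 − ρ)) × R/√12, and new dz = 0.432 / √(1 + added SD²/0.25²).

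For R = 0.6 and ρ = 0: 0.6/√12 = 0.173; added SD = 0.5 × 1.414 × 0.173 = 0.122; total SD = √(0.0625 + 0.0150) = 0.278. Variance rises by 0.0150/0.0625 = 24%, dz = 0.432/√1.24 = 0.388, and power with 44 pairs is 71.1%.

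| R | ρ | Variance increase | dz | Power, 44 pairs |
|---|---|---|---|---|
| 0.3 | 0 | 6% | 0.420 | 77.7% |
| 0.3 | 0.5 | 3% | 0.426 | 78.8% |
| 0.3 | 0.8 | 1.2% | 0.430 | 79.5% |
| 0.6 | 0 | 24% | 0.388 | 71.1% |
| 0.6 | 0.5 | 12% | 0.408 | 75.4% |
| 0.6 | 0.8 | 4.8% | 0.422 | 78.1% |
| 0.9 | 0 | 54% | 0.348 | 61.7% |
| 0.9 | 0.5 | 27% | 0.383 | 70.1% |
| 0.9 | 0.8 | 10.8% | 0.411 | 75.9% |

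With k = 0.25 instead of 0.5, R = 0.6 and ρ = 0 give 77.7%.

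**Step 3: the other anchor.** If the true paired dz is 0.865, power stays above 99% in every row of the table. The lowest case is R = 0.9, ρ = 0: 0.865/√1.54 = 0.697, power 99.5%.

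**Step 4: headroom.** If low starting plaque shrinks the true difference by a proportion a, dz becomes 0.432 × (1 − a). For a = 0.10, dz = 0.389 and power is 71%; for a = 0.25, dz = 0.324 and power is 56%. Nothing in the documents indicates a value of a, so these show sensitivity only.

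**Step 5: what the pre-floss score could recover.** In this model the post-floss score carries k times the brushing variation, so regression on the pre-floss score removes nearly all of the added variance, apart from scoring error. A plain change score carries (1 − k) times it, with opposite sign. At k = 0.5 the two multipliers are equal, so change alone gains nothing; it helps only when k exceeds 0.5.

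**The case against.** **The power figures rest on invented inputs.** This stands. The lowest figures need uncorrelated visits, which is close to a worst case: a child with a regular routine and similar appointment times would have correlated intervals. If the cited study did not control brushing either, its SD may already contain this noise, and starting from 80% would count it twice. The documents cannot settle that.

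**Analysis could recover the precision.** Largely true of the added variance. A pre-floss score appears to be taken, since Section 2.10 compares before with after. But the plan does not bring that score into the between-method contrast, and no adjustment restores headroom where there was little plaque to remove.

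**The floor effect is not shown.** Correct. No baseline plaque level is given, and score 1 already registers plaque that only a probe detects. A reader might infer that freshly brushed children arrive with nothing to score; the documents do not support going that far.

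**There is no bias.** Correct. A reader might infer that uneven brushing favours one method. Order is randomised (Section 2.5) and nothing in the documents ties brushing time to the method in use. Any general shift in brushing after the visit-1 instruction falls on both methods when the two orders are of similar size.

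**The brushing instruction already standardises hygiene.** Only in part. It does not govern timing, and being first given at visit 1 it cannot have shaped how children arrived for that visit.

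**The change comes too late.** Section 2.3 reports data collection from November 2024 to April 2025 in the past tense. For those visits only the analysis and the reporting can change.

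**Conclusion.** The concern holds as a modest, inexpensive improvement to standardisation. Time since toothbrushing is uncontrolled and unrecorded at both visits, it can differ within a child, and the planned comparison makes no allowance for it. The consequence is a possible loss of precision and headroom.

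Its size cannot be fixed from the documents. If 44 pairs give exactly 80% power, the assumed ranges lead to between 61.7% and 79.5%, depending mostly on R and ρ. If the paired effect is near 0.865, the loss does not matter. It would be wrong to read the table as showing that the trial is underpowered: that would need an SD, an effect size and a brushing-time spread that the plan does not give.

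**What to change.** In Sections 2.7 and 2.9, set one common interval between last toothbrushing and the plaque examination, identical at both visits for every child. Record the time of last brushing on arrival at both visits, and rebook a child who is outside the interval. The length of the interval is for the investigators to choose; what matters here is that it is the same.

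For visits already done, confirm that pre-floss scores exist at both visits. Then analyse the water-versus-string contrast adjusted for the pre-floss score, or as change from it; Step 5 of the working favours adjustment. Report uncontrolled brushing time as a limitation.

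For future visits the cost is one pre-visit instruction, one recorded question and occasional rebooking, with no added visits, examinations or staff. For completed visits it is a revised analysis and a sentence in the report.

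### The 24-hour no-floss condition applies only at enrolment, so starting plaque at visit 2 can differ by treatment order, and the planned comparison does not use it

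*Combined protocol and SAP*

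**What the plan says.** Section 2.7 lists, among the inclusion criteria, children "with no use of any type of dental floss within the previous 24 hours". Section 2.9 says when those criteria are used: "Participants were screened according to the inclusion and exclusion criteria".

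Section 2.2 describes both methods being used "in two separate visits with a 14-day washout period between interventions to minimize carryover effects". Section 2.9 adds: "After the first visit, a 14-day washout period was observed before the crossover intervention was applied". Neither section says what flossing was allowed between visits.

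Two kinds of teaching take place at visit 1. Brushing advice is common to everyone: "All participants received standardized oral hygiene instructions, including brushing twice daily with the Modified Bass Technique". Interdental teaching depends on the order: "Participants received instructions on the proper use of the assigned interdental cleaning method and performed the procedure independently".

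For visit 2, section 2.9 says: "At the second visit, participants switched to the opposite cleaning method (water flosser or regular floss), and plaque scores were reassessed using the same PI". The scoring rules carry over to that visit. The 24-hour condition is not mentioned there.

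Section 2.10 compares plaque scores between methods with a Wilcoxon signed-rank test and states no period, sequence or pre-floss term. A before-and-after flossing comparison is listed separately. The only regression concerns gender, adjusted for age and number of surfaces flossed.

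**The concern.** Every child uses one method at each visit, so with equal sequences half of each method's data come from visit 2. The 24-hour condition is what makes starting plaque comparable, and the plan does not require it there.

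By visit 2, children in Group A have been taught string floss and children in Group B the water flosser. What they did afterwards, including in the day before visit 2, may differ by group. Elapsed time lets the effect of a past cleaning fade, but it does not stop a newly learned habit. If starting plaque at visit 2 does differ by order, the method comparison absorbs part of that difference, and the planned test cannot separate it from a real effect.

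**Working it through.** **The plan's own figure.** Section 2.8 gives 44 children (22 per group) at 80% power and two-sided alpha 0.05, but neither the effect size nor an SD. The figure therefore cannot be reproduced. Solving backwards with t-test power, 22 per group fits a two-sample standardised difference of about 0.86, and 44 paired children fit a paired standardised difference of about 0.43. The point below does not depend on either value.

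**Where half comes from.** Let D be the water-flosser score minus the floss score in one child, and let τ be the true method effect. Let δA and δB be the visit-2 shifts in the analysed score for Group A (floss first) and Group B (water flosser first).

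- Group A has the water flosser at visit 2, so E(D) = τ + δA.
- Group B has floss at visit 2, so E(D) = τ − δB.
- The average of the two sequence means is τ + (δA − δB)/2.

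A shift common to both groups, such as one from the shared brushing advice, cancels. A shift that differs by group leaves half the difference. A period term estimates the common part only, so it leaves (δA − δB)/2 in place.

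**Simulation.** The settings were 10,000 runs, no true method effect, and within-child difference SD = 1. All shifts are assumed.

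| Visit-2 shift (SD) | Split | Bias (absolute, SD) | Signed-rank type I error |
|---|---|---|---|
| none | 22/22 | 0.00 | 4.7% |
| 0.50, both sequences | 22/22 | 0.00 | 3.0% |
| 0.50, both sequences | 28/16 (assumed) | 0.14 | 10% |
| 0.25, one sequence | 22/22 | 0.12 | 12% |
| 0.50, one sequence | 22/22 | 0.25 | 33% |
| 0.75, one sequence | 22/22 | 0.37 | 61% |
| 1.00, one sequence | 22/22 | 0.50 | 83% |

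Period adjustment restores zero bias and about 5% error in the 28/16 row. In the one-sequence rows it leaves the bias unchanged. For scale, a bias of 0.25 SD is 0.25/0.43 = 58% of the paired difference that 44 children can detect with 80% power.

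**In Plaque Index units, under assumptions only.** Suppose a share f of the children in one sequence arrive at visit 2 with PI lower by k, and flossing leaves a fraction r of the plaque. The bias in a comparison of post-floss scores is then f × k × r / 2.

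- f = 0.3, k = 0.3: 0.045 if r = 1, and 0.0225 if r = 0.5.
- f = 0.5, k = 0.5: 0.125 if r = 1, and 0.0625 if r = 0.5.

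None of f, k or r is in the documents. No PI standard deviation is given either, so this range cannot be expressed as a share of the detectable difference without a further assumption.

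**Direction.** Under the same model, within-visit reduction is smaller by (1 − r) × k in the affected children. On post-floss scores, a cleaner start favours the method used at visit 2. On reduction, it counts against that method. Section 2.10 does not say which is compared.

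**The case against.** The strongest objection is that the washout is there for this purpose: section 2.2 includes it "with a 14-day washout period between interventions to minimize carryover effects", and a washout ordinarily means that the intervention is not in use. On that reading, home flossing would be a departure from the plan. This stands in part. The washout deserves credit, but the plan gives only its length, states no conduct rule, and does not re-check the 24-hour condition at visit 2.

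A second objection is that any asymmetry between the orders is conjecture. A reader might infer that children who started with string floss kept using it at home, that children who started with the water flosser had no device to keep, and that the trial therefore favours the water flosser. The documents do not support this. They do not say whether either product was supplied, kept or used at home. If the water flosser were the one used more at home, the bias would reverse. The direction also depends on whether post-floss scores or change is compared. This objection stands in full against any claim of direction or size. It does not touch the fact that visit-2 starting plaque is uncontrolled and unused.

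Third, section 2.3 places data collection between November 2024 and April 2025, so a new question at visit 2 may come too late. That limits the procedural remedy but not the analytical one.

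**Conclusion.** The point holds as a possible bias of unknown size and direction. The documents show that the 24-hour condition applies at enrolment only, that the washout is defined by length only, that interdental teaching at visit 1 differs by order, and that the between-method test has no pre-floss term. With equal sequences, half of any order-specific difference in the analysed visit-2 score then enters the method contrast, and a period term does not remove it.

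The documents do not show that such a difference occurred. The simulated error rates rest on assumed shifts, and the PI range of 0.0225 to 0.125 rests on assumed f, k and r. Neither should be read as an estimate for this trial. A correction is still worth making, because the condition is the trial's own and the pre-floss scores needed for the analysis appear to exist.

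**What to change.** **Procedure.** Make the 24-hour no-floss condition a requirement for PI scoring at both visits: one question at visit 2, with rebooking if it is not met. State what flossing was allowed between visits.

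**Main comparison.** Use each visit's pre-floss PI, from both visits and not visit 2 alone, either as an adjustment or through within-visit change, with a period term. Specify which in advance of the analysis. Adjustment is the more flexible choice, because it estimates how far starting plaque carries into the final score. Change removes the shift fully only if r = 1 in the notation above. This relies on a pre-floss score at both visits, which the before-and-after comparison in section 2.10 implies but does not state.

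**Reporting.** Tabulate pre-floss PI by visit and sequence, so that a reader can see whether the two orders started visit 2 alike.

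**If visits are complete.** Make the analysis and reporting changes, and state whether the condition was checked at visit 2. Treat any analysis that excludes children who flossed between visits as exploratory, since it selects on behaviour after randomisation that may itself depend on order.

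**Cost.** A slightly longer interval for the few children who are rebooked, and a little more analysis work.

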2.8. Sample Size Calculation

The sample size was calculated using G*Power software (version 3.1.9.7), based on the findings of Abdellatif et al., who compared the efficacy of water flossers and regular floss in plaque removal [13]. Assuming a power of 80%, a two-tailed significance level (α) of 0.05, and an effect size derived from the cited study, a total of 44 participants (22 per group) were required to achieve sufficient statistical power.

2.9. Study Procedures

Participants were screened according to the inclusion and exclusion criteria. Parents were informed that participation was voluntary and that all collected data would remain confidential and accessible only to the research team.

Each participant was randomly assigned to start with one of the following:

- Group A: Unflavored, unwaxed regular dental floss (Oral-B, USA)(Figure 1a), or
- Group B: Water flosser (Waterpik Cordless Plus Water Flosser, USA)(Figure 1b).

After the first visit, a 14-day washout period was observed before the crossover intervention was applied.

At the first visit, demographic data (participant initials, age, and sex) and group allocation were recorded. A clinical examination was performed to assess the Plaque Index (PI) using the criteria of Silness and Le (1964). All participants received standardized oral hygiene instructions, including brushing twice daily with the Modified Bass Technique using a soft-bristled toothbrush and fluoridated toothpaste. Participants received instructions on the proper use of the assigned interdental cleaning method and performed the procedure independently.

The Plaque Index (PI) was recorded for all teeth according to the following criteria:

- 0: No plaque in the gingival area.
- 1: A film of plaque adhering to the free gingival margin and adjacent tooth area, detectable only by a probe.
- 2: Moderate accumulation of soft deposits visible to the naked eye within the gingival margin.
- 3: Abundant soft matter within the gingival pocket and/or along the gingival margin.

At the second visit, participants switched to the opposite cleaning method (water flosser or regular floss), and plaque scores were reassessed using the same PI criteria.

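### Brushing instruction given at visit 1 takes effect during the washout, so period 2 is expected to start from less plaque, which can dilute the method difference or cost the planned test power

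*Combined protocol and SAP*

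**What the plan says.** Section 2.2 describes a two-period crossover, with the methods used "in two separate visits with a 14-day washout period between interventions to minimize carryover effects". Under section 2.9 the order is random: "Each participant was randomly assigned to start with one of the following", floss or water flosser.

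The visit 1 paragraph of section 2.9 lists three steps in this order:

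1. "A clinical examination was performed to assess the Plaque Index (PI) using the criteria of Silness and Le (1964").
2. "All participants received standardized oral hygiene instructions, including brushing twice daily with the Modified Bass Technique".
3. "Participants received instructions on the proper use of the assigned interdental cleaning method and performed the procedure independently".

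For visit 2 the text says that the children switched method and that "plaque scores were reassessed using the same PI criteria". It does not separately describe a pre-flossing score at that visit. No section describes a run-in or brushing instruction before visit 1. The index runs from 0 to 3, and its lowest category is "0: No plaque in the gingival area".

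Section 2.10 compares the methods with a Wilcoxon signed-rank test on paired scores. It has no period, sequence or baseline term. It also lists comparisons of scores before and after flossing, so some pre-flossing scores exist.

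**The concern.** A washout should bring the child back to the same starting state before the second method. Here every child is taught a plaque-reducing routine at visit 1 and is meant to follow it through those 14 days. The washout can clear residual effects of the first interdental method, but it cannot clear a taught behaviour to which it gives time to act.

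The instruction comes after the visit 1 plaque examination, so it cannot have standardized the plaque on which period 1 is tested. Period 1 tests the methods on the child's usual plaque. Period 2 tests them on plaque that two weeks of taught brushing may have lowered. Half of the data for the main comparison would then come from a different plaque condition. The averaged difference may be smaller than the one under usual plaque, or it may be estimated with extra noise that the planned test does not remove.

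**Working it through.** **Inputs from the documents.** 44 participants (22 per group), two-sided alpha 0.05, power 80% (section 2.8); index 0–3 (section 2.9); Wilcoxon signed-rank test without a period or baseline term (section 2.10).

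**Inputs not in the documents.** The effect size, the SD, the visit 2 starting plaque and the way plaque is removed. These are assumed below and shown over a range.

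**The plan's own figure.** The 44 cannot be reproduced forward, because section 2.8 takes the effect size from a cited study without stating it. Solving backward for 80% power with the noncentral t gives:

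- 44 pairs, paired t: standardized paired difference dz = 0.432.
- 22 per group, two-sample t: d = 0.865. This equals dz = 0.865 if the within-child correlation is 0.5, since the SD of a difference is SD × √(2(1 − 0.5)) = SD.

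**Mechanism (a): each method removes a share of the plaque present.** Let f be the visit 2 starting plaque as a fraction of visit 1. The period 2 difference is f times the period 1 difference, so the average is (1 + f)/2 of the period 1 difference.

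- 20% drop: (1 + 0.80)/2 = 0.90
- 33% drop: (1 + 0.67)/2 = 0.835
- 50% drop: (1 + 0.50)/2 = 0.75

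A simulated crossover with 22 children per sequence (assumed starting plaque 1.5, removal 45% versus 55%) agrees:

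| f | Period 1 difference | Period 2 difference | Unadjusted estimate | With additive period term | Percent-reduction difference |
|---|---|---|---|---|---|
| 1.0 | 0.150 | 0.150 | 0.150 | 0.150 | 0.10 |
| 0.8 | 0.150 | 0.120 | 0.135 | 0.135 | 0.10 |
| 0.6 | 0.150 | 0.090 | 0.120 | 0.120 | 0.10 |

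The period term changes nothing, because the shrinkage is a treatment-by-period interaction. Percent reduction from the same-visit starting score recovers the same effect at every f.

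**Power under (a)**, paired t with 44 pairs, taking the shift in level between visits as already removed:

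- SD constant: dz × (1 + f)/2.
- SD scaling with plaque (independent errors in the two periods): the SD of the difference is multiplied by √((1 + f²)/2), which is 0.906, 0.851 and 0.791. The net factors on dz are 0.90/0.906 = 0.994, 0.835/0.851 = 0.981 and 0.75/0.791 = 0.949.

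| Drop | dz 0.432, SD constant | dz 0.432, SD scales | dz 0.865, SD constant |
|---|---|---|---|
| 20% | 71.3% | 79.5% | 99.9% |
| 33% | 64.8% | 78.5% | 99.7% |
| 50% | 55.6% | 75.7% | 98.8% |

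**Mechanism (b): each method removes a fixed amount and visit 2 is only shifted down.** The difference stays at 0.150 in both periods. The shift adds to the paired difference in one sequence and subtracts from it in the other, so it inflates the spread that the unadjusted test sees. With dz = 0.432, simulated power for a visit 2 shift of 0, 0.5, 1.0 and 1.5 SD of the paired difference is about 78%, 70%, 46% and 18% for the planned Wilcoxon test. A period-adjusted rank-sum test stays at about 78–79%.

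**The case against.** The documents report no visit 2 starting plaque, no adherence to the taught brushing and no removal model. Lower plaque at visit 2 is an expectation, and shrinkage of the difference needs a further assumption: proportional removal or scores near the floor. This stands, and the point is conditional for that reason. It does not dispose of the point, because under a plain shift the planned test still loses power.

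Three stronger readings are tempting and are not supported.

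- A reader might infer that the comparison is biased toward one method. Order is randomized and every child gets the same instruction. With balanced sequences the result is dilution and lost power, and neither method gains.
- A reader might infer that no analysis can repair the damage. Under proportional removal, percent reduction from the same-visit starting score gives the same method effect at every plaque level tested, and a comparison of period 1 alone largely avoids the problem. What fails is the washout and a purely additive period term. Section 2.10 shows that some pre-flossing scores exist; whether they exist at both visits is unclear from section 2.9.
- A reader might infer that the trial is clearly underpowered, or that a null result could be put down to the brushing instruction alone. The low power figures need both dz = 0.432 and a constant SD. Even at a 50% drop, 75% of the difference remains.

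It can also be said that common brushing instruction is a reasonable way to standardize children. That would carry weight if it came before period 1 with time to act. Given after the visit 1 examination, it cannot standardize the plaque on which period 1 is tested.

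**Conclusion.** The concern holds in conditional form. Section 2.9 places a plaque-reducing instruction so that its effect falls in the washout, and period 2 is expected to start from less plaque than period 1.

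Under proportional removal, the average method difference is about 90%, 84% or 75% of its period 1 size for assumed drops of 20%, 33% or 50%. Under a plain shift it is not diluted, but the unadjusted Wilcoxon test pays in power. The power loss under proportional removal runs from negligible (dz 0.865, about 99% or more) through small (76% to 80% if the SD scales with plaque) to material (56% to 71% at dz 0.432 with constant SD). The documents do not allow a choice among these, since neither the effect size nor the visit 2 plaque level is given.

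**What to change.** In the design, keep the general brushing instruction out of the interval between the two scored periods. Give it after the last visit 2 plaque score, and at visit 1 teach only the use of the assigned interdental method. This re-times one procedure and needs no added visit or staff. The cost is that children receive the general advice about 14 days later and brush in their usual way until then.

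Section 2.3 describes data collection as complete, so where the instruction was already given at visit 1 the remedy lies in analysis and reporting:

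- State whether a pre-flossing plaque score was recorded at both visits, and report its level by visit.
- Where it was recorded, compare the methods on change or percent reduction from the same-visit pre-flossing score, with a period term. Percent reduction suits proportional removal and change suits removal of a fixed amount. Showing both reveals whether the conclusion depends on that choice.
- Report the method difference separately for each period.

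This costs some extra analysis and no new data. If visit 2 pre-flossing scores were not taken, only the period term and the by-period results remain available, and the report should say so.
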